2. LIST OF ABBREVIATIONS

Term	Definition / Description
AE	Adverse Event
BHM	Bayesian Hierarchical Model
BOR	Best Overall Response
CR	Complete Response
CTC	Common Terminology Criteria
CTP	Clinical Trial Protocol
CTR	Clinical Trial Report
DM&SM	Boehringer Ingelheim Data Management And Statistics Manual
DLT	Dose Limiting Toxicity
DoR	Duration of Response
DRA	Drug Regulatory Affairs
DMG	Dictionary Maintenance Group
eCRF	Electronic Case Report Form
EDC	Electronic Data Capture
EMEA	European Agency For The Evaluation Of Medicinal Products
FAS	Full Analysis Set
GBM	Glioblastoma
GEP	Gene-Expression Profile
ICH	International Conference On Harmonisation
IPD	Important Protocol Deviation
LOCF	Last Observation Carried Forward
MedDRA	Medical Dictionary For Regulatory Activities
MQRM	Medical Quality Review Meeting
NOA	Not Analysed
NOR	No Valid Result
NOS	No Sample
NSCLC	Non-Small Cell Lung Cancer
OR	Objective Response

Term	Definition / Description
OS	Overall Survival
PD	Protocol Deviation
PFS	Progression-Free Survival
PFS6	Six-Month Progression-Free Survival
PK	Pharmacokinetics
PKS	PK Analysis Set
PPS	Per Protocol Set
PR	Partial Response
PSTAT	Project Statistician
PT	Preferred Term
Q1	Lower Quartile
Q3	Upper Quartile
RANO	Response Assessment in Neuro-Oncology
RECIST	Response Evaluation Criteria In Solid Tumours
REP	Residual Effect Period
RP2D	Recommended Phase 2 Dose
RPM	Report Planning Meeting
SA	Statistical Analysis
SD	Standard Deviation
SMC	Safety Monitoring Committee
SMQ	Standardized MedDRA Query
SOC	System Organ Class
SSC	Special Search Category
TCM	Trial Clinical Monitor
TESS	Treatment Emergent Signs And Symptoms
ToC	Table of Contents
TMW	Trial Medical Writer
TS	Treated Set
TSAP	Trial Statistical Analysis Plan

[figure not shown]
3. INTRODUCTION

As per ICH E9 ([1](#)), the purpose of this document is to provide a more technical and detailed elaboration of the principal features of the analysis described in the protocol and to include detailed procedures for executing the statistical analysis of the primary and secondary variables and other data.

This TSAP assumes familiarity with the Clinical Trial Protocol (CTP), including Protocol Amendments. In particular, the TSAP is based on the planned analysis specification as written in CTP Section 7 “Statistical Methods and Determination of Sample Size”. Therefore, TSAP readers may consult the CTP for more background information on the study, e.g., on study objectives, study design and population, treatments, definition of measurements and variables, planning of sample size, and randomization.

SAS® Version 9.4 or the latest version will be used for analyses.

R Version 3.5.1 and JAGS Version 4.3.0 or the latest versions will be used for the BLRM and BHM analyses.

5. ENDPOINT(S)

This is a Phase Ib study containing two parts: Part 1 (dose escalation of BI 836880 in combination with ezabenlimab (BI 754091)) and Part 2 (expansion at the RP2D in 8 cohorts with different tumour types and line of therapy) in patients with locally advanced or metastatic non-squamous NSCLC and in other solid tumors.

The primary objective for Part 1 is to determine the safety and tolerability of BI 836880 in combination with ezabenlimab and find the Maximum Tolerated Dose (MTD)/Recommended Phase 2 Dose (RP2D).

The primary objective for Part 2 is to assess the anti-tumor activity of BI 836880 in combination with ezabenlimab in patients with locally advanced or metastatic non-squamous NSCLC and in other solid tumors.

5.1 PRIMARY ENDPOINT(S)

PART 1:

The primary endpoint is the number of patients with dose limiting toxicities (DLTs) within the MTD evaluation period, which will be assessed for dose escalation in order to determine the maximum tolerated dose (MTD) of the combination of BI 836880 and ezabenlimab.

The MTD is defined as the highest dose with less than 25% risk of the true DLT probability being above 33% and may be considered reached if the probability that the true DLT rate is in the target interval (16%-33%) is sufficiently large during the MTD evaluation period.

The definition of DLTs for solid tumour patients is provided in Section 5.2.6.1 of the CTP.

The MTD evaluation period is defined as the time from the first administration of study treatment to the start of the second treatment cycle, i.e., the first treatment cycle.

PART 2:

The primary endpoint is Objective Response (OR) defined as best overall response (RECIST 1.1) of complete response (CR) or partial response (PR) from first treatment infusion until the earliest of disease progression, death, or last evaluable tumor assessment before start of subsequent anti-cancer therapy, lost to follow-up, or withdrawal of consent. In the case of recurrent glioblastoma (GBM), tumour assessment will be based on RANO (Response Assessment in Neuro-Oncology) criteria.

5.2 SECONDARY ENDPOINT(S)

5.2.1 Key secondary endpoint(s)

This section is not applicable, as no key secondary endpoint has been specified in the protocol.

[figure not shown]
5.2.2 Secondary endpoint(s)

PART 1:

- Adverse events (AEs), drug related AEs, drug related AEs leading to discontinuation during treatment period.
- Pharmacokinetic parameters C_{max} , T_{max} , and AUC_{0-504h} after the first and fourth infusion cycle.

PART 2:

- Adverse events (AEs), drug related AEs, drug related AEs leading to discontinuation during treatment period.
- Disease control (DC), defined as best overall response of CR, PR, or stable disease (SD) by RECIST 1.1 (RANO for the GBM cohort) from start of treatment infusion until the earliest of disease progression, death, or last evaluable tumor assessment before start of subsequent anti-cancer therapy, lost to follow-up, or withdrawal of consent.
- Duration of objective response (DoR), defined as the time from first documented CR or PR by RECIST 1.1 (RANO for the GBM cohort) until the earliest of disease progression or death among patients with OR.
- Progression-free survival (PFS) (RANO for the GBM cohort and RECIST 1.1 for all other cohorts), defined as the time from first treatment infusion until disease progression or death from any cause, whichever occurs earlier.
- Tumor shrinkage (in millimeters), defined as the difference between the minimum post-baseline sum of diameters of target lesions (longest for non-nodal lesions, short axis for nodal lesions) and the baseline sum of diameters of the same set of target lesions. In GBM, using RANO criteria, tumor shrinkage will be calculated based on the difference between the post-baseline and baseline measurements of the sum of product of the largest bi-dimensional measurements for all target lesions.
- Pharmacokinetic parameters C_{max} , T_{max} , and AUC_{0-504h} after the first infusion cycle.

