7.5 SECONDARY ENDPOINT(S)

[figure not shown]
The analysis of secondary endpoints will be performed as defined in the CTP.

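### Tumour shrinkage in Part 2 has no assessment window, and its GBM version has the wrong unit and does not say which scan counts

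*SAP*

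**What the plan says.** SAP section 5.2.2 lists tumour shrinkage among the Part 2 secondary endpoints. For the RECIST cohorts it starts from "Tumor shrinkage (in millimeters), defined as the difference between the minimum post-baseline sum of diameters of target lesions" and subtracts the baseline value: "and the baseline sum of diameters of the same set of target lesions". There is no division by baseline.

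The same bullet then gives a separate rule for GBM under RANO: the "difference between the post-baseline and baseline measurements of the sum of product of the largest bi-dimensional measurements for all target lesions". No further unit is given.

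Two other tumour endpoints state when assessment ends. Objective response (section 5.1) runs "until the earliest of disease progression, death, or last evaluable tumor assessment before start of subsequent anti-cancer therapy, lost to follow-up, or withdrawal of consent". Disease control, in the same list as tumour shrinkage, runs "from start of treatment infusion until the earliest of disease progression, death, or last evaluable tumor assessment before start of subsequent anti-cancer therapy", with the same closing conditions.

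On analysis, section 7.5 says only: "The analysis of secondary endpoints will be performed as defined in the CTP". Section 7.5.2 is marked as not applicable.

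**The concern.** There are three weaknesses in one definition, of unequal weight.

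- **No window.** The RECIST rule takes a minimum over every post-baseline sum. Followed literally, a sum measured after progression or during the next line of treatment is eligible. Shrinkage that the study drugs did not produce could then be counted as theirs.
- **GBM unit and scan.** The only unit in the bullet does not fit an area. Without a minimum, the GBM sentence does not say which of the repeated scans is compared with baseline. The first, the last and the best scan all satisfy the text, so two programmers could produce different GBM results.
- **Scale.** An absolute change in millimetres depends on how much tumour the patient had at the start, so cohort summaries partly reflect baseline burden.

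**Working it through.** The SAP states no figure for this endpoint, so there is nothing to reproduce. The check compares the definitions and then uses assumed values. Every lesion measurement below is an assumption, not a figure from the SAP.

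**1. Windows side by side**

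| Endpoint | SAP section | End of assessment |
|---|---|---|
| Objective response | 5.1 | Progression, death, or last evaluable scan before new therapy, loss to follow-up or withdrawal |
| Disease control | 5.2.2 | Same as objective response |
| Duration of response, PFS | 5.2.2 | Progression or death |
| Tumour shrinkage | 5.2.2 | None stated; "the minimum post-baseline sum of diameters of target lesions" |

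Section 6.7 does not supply the limit. It assigns scans to Week 6, 12, 18 and so on with a window of 3 weeks either side, but excludes none.

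**2. Direction and possible size of the window effect**

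The minimum over a longer series is never above the minimum over a shorter series contained in it. Adding later scans therefore leaves the value unchanged or makes it more favourable.

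Assume a baseline of 100 mm, then 90 mm, then 125 mm (progression), then 50 mm under new therapy.

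- As worded: min(90, 125, 50) - 100 = 50 - 100 = -50 mm.
- Stopping at progression: min(90, 125) - 100 = 90 - 100 = -10 mm.

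The difference is 40 mm in this patient, all of it from the scan on new therapy. Whether the progression scan itself is counted makes no difference here, because 90 is the smaller value either way.

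**3. GBM unit**

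Assume one lesion shrinking from 40 x 30 mm to 30 x 20 mm.

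- In millimetres: (30 x 20) - (40 x 30) = 600 - 1200 = -600 mm².
- In centimetres: (3 x 2) - (4 x 3) = 6 - 12 = -6 cm².
- Percentage: 100 x (600 - 1200) / 1200 = -50%, in either unit.

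The absolute result is an area whichever length unit is used. Only the percentage is free of the unit.

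**4. Dependence on baseline burden (RECIST cohorts)**

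Percentage change = 100 x (minimum - baseline) / baseline, for the same absolute change of -20 mm:

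| Baseline (mm) | Minimum (mm) | Absolute (mm) | Percentage |
|---|---|---|---|
| 25 | 5 | -20 | -80.0% |
| 50 | 30 | -20 | -40.0% |
| 100 | 80 | -20 | -20.0% |
| 150 | 130 | -20 | -13.3% |
| 200 | 180 | -20 | -10.0% |

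Over this assumed range, one absolute value stands for relative changes from -80% to -10%.

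**The case against.** The strongest reply is that the protocol, which is not at hand, may set the window. SAP section 3 sends readers there for definitions of variables, and section 7.5 does so for the analysis of secondary endpoints. Nothing in the SAP shows that target lesions are measured after progression or under new therapy. The endpoint is not a key secondary one, and the SAP attaches no test or decision rule to it.

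Much of this stands, and it limits the size of the point. It does not remove it. The SAP writes this definition out in full, as it does for objective response and disease control, and gives a window for those two but not here. Duration of response and PFS also lack a clause on subsequent therapy, but both end at progression or death.

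A second reply is that an absolute change is a legitimate, reproducible choice. That also stands: the RECIST rule is clear as to unit and baseline, and nothing in the SAP contradicts it.

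A third is that no analyst would label a product of diameters in millimetres, since the unit stands only at the head of the bullet. That may be so for the unit, but it does not settle which GBM scan is used.

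A reader might also infer three stronger things that the SAP does not support:

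- *Millimetre changes cannot be compared between patients.* They share a unit across the RECIST cohorts and can be compared. They are only sensitive to baseline burden.
- *GBM areas are mixed with diameters from other cohorts.* Section 6.1 displays Part 2 data separately by cohort. A numerical ratio between an area change and a length change would also mean little, because it depends on the unit chosen.
- *Shrinkage will be overstated.* That requires late scans in the database, which the SAP does not show.

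**Conclusion.** The point holds as a defect of definition in a secondary endpoint, worth correcting before database lock. The primary endpoint and disease control have their own windows and are unaffected.

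- **Window:** absent here, present for objective response and disease control. Any effect is in the favourable direction only. Its size is unknown; the 40 mm gap above illustrates one assumed patient and is not an estimate for the trial. It is conditional on target-lesion scans after progression or under new therapy being in the database, and on no limit being applied from the protocol.
- **GBM:** the unit mismatch and the undefined scan follow from the SAP text alone, with no assumption. They concern one cohort.
- **Scale:** a weak choice, not an error or a contradiction.

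**What to change.** Amend the tumour shrinkage bullet in SAP section 5.2.2:

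1. Restrict the minimum to assessments within the window used for objective response and disease control, and say whether the scan that declares progression is counted.
2. For GBM, define the quantity from the minimum post-baseline sum of products and give it an area unit.
3. Add best percentage change from baseline, (minimum post-baseline - baseline) / baseline x 100, reported by cohort. Use sums of diameters for the RECIST cohorts and sums of products for GBM. Keep the absolute change already defined alongside it.

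If the protocol's definition differs, record the amendment as a change from it. The cost is wording and one extra derived variable, with no new data. Shrinkage values may come out slightly less favourable if late scans had been contributing.

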6. GENERAL ANALYSIS DEFINITIONS

6.1 TREATMENT(S)

In this open-label Phase Ib trial, treatments are not randomized. In the dose escalation part (Part 1), the starting dose combination is BI 836880 360 mg + ezabenlimab (BI 754091) 240 mg every three weeks. Dose escalation is only performed for BI 836880. Ezabenlimab is fixed at dose 240 mg. Dose escalation decisions will be made by the Safety Monitoring Committee (SMC). Based on the dose escalation data in Part 1, the SMC will select one combination dose for the expansion cohorts in Part 2. Data of the dose expansion part (Part 2) will be displayed separately for each of the multiple cohorts.

For the dose escalation part (Part 1), the initial trial medication (i.e., dose level) assigned at the beginning of the first treatment cycle will be used as the label of the analysing treatment.

For safety analyses, adverse events (AEs) will be displayed separately within the following time periods: “Screening”, “On-treatment”, or “Post-study” (see Table 6.1: 1). This will be applied for both AEs and immune-related AEs. Refer to CTP Section 5.2.7.2 for details of AE collection and reporting.

Table 6.1: 1 Definition of treatment periods

Analysing Treatment Period	Start Date (including)	Stop Date (excluding)
Screening	Date of informed consent	The date of first trial medication administration - 1 day
On-treatment	Date of first administration of trial medication	Date of last trial medication administration + REP, or death, or DBL date, whichever comes first i.e., actual on-treatment period + REP,
Post-study	Last day of on-treatment period +1 day	Date of the last contact date or death, or DBL date, whichever comes first

Note: A 42-day residual effect period (REP) is defined for both Parts 1 and 2.

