7.8.1 Adverse events

The analyses of adverse events (AE) will be descriptive in nature. All analyses of AEs will be based on the number of patients with AEs and not on the number of AEs. Two analyses will be performed. The first analysis of safety will be performed for the first part of the trial (determination of the MTD/RP2D, first cycle only, dose level = initial dose at the start of the treatment, treated set). This descriptive analysis will evaluate the MTD/RP2D. The second analysis will be performed with respect to all cycles for part 1 and will act as a support for the determination of the MTD/RP2D (treated set).

For analysis of duration, severity, etc. of multiple AE occurrences, data on the case report form (CRF) will be collapsed into AE episodes provided that all of the following applies:

- The same MedDRA lowest level term was reported for the occurrences.
- The occurrences were time-overlapping or time-adjacent (time-adjacency of two occurrences is given if the second occurrence started on the same day or on the day after the end of the first occurrence).
- Treatment did not change between the onset of the occurrences or treatment changed between the onsets of the occurrences, but no deterioration was observed for the later occurrence.

For further details on summarization of AE data, please refer to the guideline 'Handling and summarization of adverse event data for clinical trial reports and integrated summaries' ([5](#)).

For patients treated with the test drug, that means that all adverse events occurring between first drug infusion and the REP after last drug infusion or death, whichever occurs first, will be assigned to the on-treatment period. All adverse events occurring before any study drug infusion will be assigned to 'screening' and all adverse events occurring after last study drug infusion + the REP will be assigned to 'post-study' (for listings only). For details on the treatment definition, see [Section 6.1](#).

An overall summary of adverse events will be presented. This summary will exclude the rows 'Severe AEs', 'Significant AEs' and 'Other significant AEs' but will include additional rows for 'AEs leading to dose reduction', 'AEs leading to death' and 'AEs by highest Common Terminology Criteria (CTC) grade'.

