Additional AE tables will be produced for AEs of special interest (hepatic injury as defined in CTP Section 5.2.7.1 and DLTs as defined in CTP Section 5.2.6.1), providing further details on highest CTC grade, action taken with study drug, and time to first onset of AE.

The frequency of patients with adverse events will be summarized by maximum CTC grade (grades 1, 2, 3, 4, 5 and all grades), treatment, primary system organ class and preferred term for each of the following AE tables as well as relatedness of AEs to treatment and seriousness:

- All AEs

- Drug-related AEs
- Immune-related AEs
- AEs leading to dose reduction
- Drug-related AE leading to dose reduction
- Immune-related AEs leading to dose reduction
- AEs leading to treatment discontinuation
- Drug-related AEs leading to treatment discontinuation
- Immune-related AEs leading to treatment discontinuation
- Drug-related AEs leading to treatment discontinuation or dose reduction
- Immune-related AEs leading to treatment discontinuation or dose reduction
- AEs leading to death
- Serious AEs
- Drug-related serious AEs
- AESIs
- DLTs (in Part 1 dose escalation only)

All tables will be sorted by system organ class (SOC) according to the standard sort order specified by the European Medicines Agency (EMA). Preferred terms (PTs) will be sorted by frequency (within SOC).

The above tables will be repeated with the project-defined grouping of AE terms. Details of the project-defined groupings are defined in the technical TSAP. In these tables, the grouped AEs will replace the original PTs for all AEs that are included within the grouped term. The grouped AE categories will then be tabulated along with all remaining MedDRA PTs, sorted by descending frequency.

A reference table presenting the entire project defined groupings and MedDRA PTs within each grouping will also be produced.

The frequency of patients with user defined AEs will be presented by special search category, preferred term, and highest CTCAE grade. Special search categories (SSCs) for AEs are defined in Table 7.8.1: 1 below.

Table 7.8.1: 1 Definitions of SSCs

N	Medical concept	Definition (for programmers)	Other monitoring options
1	Fatigue / asthenia	HLT 10003550	
2	Hypertension	SMQ 20000147	Narrow
3	Proteinuria	SMQ 20000220	Narrow
4	Haemorrhage	SMQ 20000040 SMQ 20000039	Narrow Narrow
5	Embolic and thrombotic events	SMQ 20000081 SMQ 20000115	Narrow Narrow and broad
6	GI perforation	SMQ 20000107	Narrow

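### Immune-related AEs, and drug-related serious or fatal AEs, that start after the 42-day residual effect period are only listed and enter no AE frequency table (minor; cheap to improve)

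*SAP*

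**What the plan says.** Section 6.1 states that AEs "will be displayed separately within the following time periods": screening, on-treatment and post-study. It adds: "This will be applied for both AEs and immune-related AEs". In Table 6.1: 1 the on-treatment period ends at "Date of last trial medication administration + REP, or death, or DBL date, whichever comes first". The note to the table gives a single value: "A 42-day residual effect period (REP) is defined for both Parts 1 and 2". The post-study period then runs to last contact, death or database lock.

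Section 7.8.1 fixes what happens to later events: "all adverse events occurring after last study drug infusion + the REP will be assigned to 'post-study' (for listings only". The sentence makes no exception for immune-related, drug-related, serious or fatal events.

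The same section lists the frequency tables, introduced by "The frequency of patients with adverse events will be summarized by maximum CTC grade". Four concern immune-related AEs: all such events, those leading to dose reduction, those in the row "Immune-related AEs leading to treatment discontinuation", and those leading to either action. Others cover drug-related serious AEs and AEs leading to death. Tables 7.8.1: 1 and 7.8.1: 2 add special search categories, the second set specific to combinations with ezabenlimab. No table is given a longer window, and none is planned for the post-study period.

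**The concern.** The SAP treats immune-related toxicity as a topic of its own: it has its own tables, and ezabenlimab has its own search categories. The SAP also defines a post-study period for these events and expects some of them to be available for listing. Yet an event in that period adds nothing to any patient count or maximum-grade count.

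At stake is how completely the tables describe the combination's safety. A reader of the trial report who relies on them would not see a patient whose only immune-related event began after the REP, nor a late fatal event judged related to treatment, unless that reader also worked through the listings. Laboratory data are handled differently: Section 7.8.2 plans summaries for the post-treatment period as well.

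**Working it through.** The SAP states no figure to reproduce. The check sets the rules side by side.

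**Inputs**
- REP: 42 days, both parts (Section 6.1, note to Table 6.1: 1).
- Dosing interval: "ezabenlimab (BI 754091) 240 mg every three weeks", that is 21 days (Section 6.1).
- DLT window: the first treatment cycle (Section 5.1).
- Counting unit: patients with AEs, not AEs (Section 7.8.1).
- Post-study AEs: listings only (Section 7.8.1).

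**Step 1: the cut-off.** 42 / 21 = 2, so the counted period closes two dosing intervals after the last infusion. An event starting from about day 43 after the last infusion is post-study. (Table 6.1: 1 labels its stop date as excluded, which could move the boundary by a day; this does not matter here.)

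**Step 2: which patients are affected.** Because patients are counted by maximum grade, the result depends on what the patient already had during the on-treatment period, for the table row concerned:

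| On-treatment event | Event starting after the REP | Shown in the frequency table |
|---|---|---|
| None | Any grade | Patient absent |
| Lower grade | Higher grade | Patient counted, grade too low |
| Same or higher grade | Any grade up to that | No effect |
| Any | None | No effect |

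Only the first two patterns lose information. Events that begin late in treatment, or within 42 days of the last infusion, are counted.

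**Step 3: which tables are affected.**
- Exposed: the general immune-related AE table, drug-related serious AEs, AEs leading to death, and the special search categories.
- Not exposed: the Part 1 DLT endpoint. The first cycle lasts 21 days, and the on-treatment period lasts at least 42 days from the first infusion unless death or database lock ends it.
- In practice not exposed: the discontinuation and dose-reduction tables. An event starting more than 42 days after the last infusion will not ordinarily have caused dosing to be reduced or stopped. The possible exception is a patient whose dosing had been on hold for that long.

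**Step 4: size.** The SAP gives no distribution of onset times. Let f be the share of patients with a collected immune-related AE whose only such event starts after the REP. Then

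tabulated incidence = (1 − f) × collected incidence.

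With f purely as an assumption:
- f = 0 (for example, nothing collected after the REP): 100% of collected incidence
- f = 5%: 95%
- f = 10%: 90%
- f = 20%: 80%

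These values show how the rule works; they do not estimate the effect in this trial.

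**The case against.** The strongest reply is that this is a deliberate, consistent convention. Section 6.1 explicitly includes immune-related AEs, Section 7.8.1 follows it, and later events are still reported in listings. AE tables bounded by a residual period are legitimate. AE collection is left to CTP Section 5.2.7.2, which was not available for this review, so the loss could be nil. In addition, Section 5.2.2 ties its safety endpoints to the treatment period, at least for drug-related AEs leading to discontinuation, and does not name immune-related AEs as an endpoint. All of this stands. It limits the point to a supplement and does not call for replacing the tables.

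A reader might also infer more than the SAP supports:
- **That 42 days is demonstrably too short for this agent.** The SAP gives no half-life and no onset data from which to judge that.
- **That incidence is understated by a known percentage, or by the share of events that start late.** No such share is given. Patients are counted, so a late event in a patient already counted at the same or a higher grade changes nothing in that row.
- **That cohorts with fast progression will look safer because of the REP.** A patient with infusions on Days 1 and 22 is counted to about Day 22 + 42 = 64. A patient with ten infusions is counted to about Day (1 + 9 × 21) + 42 = 190 + 42 = 232. Both have the same 42 days after the last infusion; the difference is treatment duration. Counting to last contact would still leave unequal follow-up. AE analysis is descriptive.
- **That Sections 6.1 and 7.8.1 contradict each other.** Section 6.1 speaks of separate display by period, and Section 7.8.1 specifies that the post-study display is a listing.

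**Conclusion.** The point holds in a limited form, as a minor matter. Under the stated rules, a patient whose first or worst immune-related AE, or whose drug-related serious or fatal AE, starts after the REP is missing from, or under-graded in, the exposed tables. That follows from the text and needs no outside premise.

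The size of the undercount cannot be determined from the SAP. It rests on two unknowns: what the protocol collects after the REP, and how many patients have such an event with no on-treatment event, or only a lower-grade one, in the same row. The rule can understate these counts; whether it does so materially in this trial is not shown.

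**What to change.** Keep Table 6.1: 1 and all standard tables as they are. Add to Section 7.8.1 one supplementary table that counts patients with
- immune-related AEs, and
- drug-related serious or fatal AEs,

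with onset at any time from first administration to last contact. Show it by maximum CTC grade and by period (on-treatment, post-study), and flag events that start after subsequent anti-cancer therapy.

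The cost is one extra table built from data already intended for the listings. No clinical rule changes. The small downside is that collection after the REP may be less complete than on treatment; a footnote should say so and state the protocol's collection period for these events. If the protocol collects none of them after the REP, one sentence in Section 7.8.1 saying so would be enough.

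### SAP Table 6.1: 1 and Section 7.8.1 disagree at the treatment-period boundaries, and the table leaves the day of an on-treatment death in no period

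*SAP*

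**What the plan says.** Section 6.1 sends the display of AEs by period to Table 6.1: 1. Its start dates are labelled as included. Its stop column is headed "Stop Date (excluding" (closing bracket follows), so a stop date is not part of its period. The three rows are:

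- **Screening** runs from informed consent to "The date of first trial medication administration - 1 day".
- **On-treatment** runs from "Date of first administration of trial medication" to "Date of last trial medication administration + REP, or death, or DBL date, whichever comes first".
- **Post-study** runs from "Last day of on-treatment period +1 day" to "Date of the last contact date or death, or DBL date, whichever comes first".

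A note under the table sets the REP at 42 days for both parts.

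Section 7.8.1 gives a second rule in words. "All adverse events occurring before any study drug infusion will be assigned to" screening. Events between the first infusion and "the REP after last drug infusion or death, whichever occurs first, will be assigned to the on-treatment period". Events after the last infusion plus the REP are post-study and appear in listings only. The same paragraph then refers to Section 6.1 for details of the treatment definition, and Section 7.8.2 does likewise for the laboratory summaries.

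**The concern.** The two rules give different answers on specific days, and the SAP does not rank them. The day of death matters most. An AE whose onset and death fall on the same date is usually a sudden fatal event. Table 7.8.1: 1 names categories where this can happen, such as haemorrhage, embolic and thrombotic events, and GI perforation. Such events feed the row for AEs leading to death in the overall summary and the grade 5 column of the frequency tables. AEs during the treatment period are also a secondary endpoint in both parts (Section 5.2.2), so this boundary helps to define a reported endpoint. Because the AE section points back to the table, a programmer could reasonably implement the table as written.

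**Working it through.** No sample size or error rate is involved. The check is whether each calendar day falls in exactly one period.

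**Notation.** C = consent, F = first dose, L = last dose, X = death, K = last contact, B = database lock (DBL), d = AE onset day.

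**Table 6.1: 1, read literally** (start included, stop excluded):

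- Screening: C ≤ d < F − 1
- On-treatment: F ≤ d < S, with S = min(L + 42, X, B)
- Post-study: P ≤ d < min(K, X, B). P = S + 1 if the last on-treatment day means the stop date, and P = S if it means the last day counted, S − 1.

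**Section 7.8.1, at date level:** before F is screening; from F to min(L + 42, X) is on-treatment; after L + 42 is post-study.

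**General result.**

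1. *Death within the REP.* Here S = X, and d = X fails d < X, so the death day is not on-treatment. Post-study starts at X or X + 1 and stops, excluded, no later than X, so it is empty. Day X has no period under either reading of P. Under Section 7.8.1, day X is neither before the first infusion nor after L + 42, so on-treatment is the only class left.
2. *Day L + 42 in a patient who lives past it.* The table excludes it from on-treatment. It has no period if P = S + 1, and is post-study (listings only) if P = S. Section 7.8.1 moves only later events to post-study, so it keeps this day on-treatment.
3. *Day F − 1.* It fails d < F − 1 and precedes F, so it has no period in the table. Section 7.8.1 calls it screening.
4. *Last contact day and DBL day.* Each is an excluded stop, so it is unassigned in the same way when it ends the post-study period.
5. *Day F, before the infusion.* It is on-treatment in the table and screening in Section 7.8.1.

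**Worked patient (assumed dates).** C = −10, F = 0, L = 42, so L + 42 = 84; DBL is late (day 400). The table lists the days in no period.

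| Outcome | Table, P = S + 1 | Table, P = S | Table with stop dates included | Section 7.8.1 |
|---|---|---|---|---|
| Death on day 60 | −1, 60 | −1, 60 | none | none (day 60 on-treatment) |
| Death on day 120 | −1, 84, 120 | −1, 120 | none | none (day 120 post-study) |
| Alive, last contact day 150 | −1, 84, 150 | −1, 150 | none | none (day 150 post-study) |

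With stop dates included and post-study starting the next day, every day is assigned once and the result agrees with Section 7.8.1 at date level. Item 5 remains open, because it turns on the time of the event within the day.

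**Effect on the tables.** Only items 1 and 2 can remove an event from the on-treatment tables. Suppose f patients have a fatal on-treatment AE, and in k of them the only such AE began on the day of death. The literal table would then report f − k, an understatement of k/f. The document gives neither k nor f, so the fraction can lie anywhere from 0 to 1.

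**The case against.** The strongest reply is that Section 7.8.1, the section on AEs, already assigns every event. Pre-infusion events are screening, events up to the end of the REP or death are on-treatment, and later ones are post-study. The table itself also hints that only its heading is wrong. A screening stop one day before first dose and a post-study start one day after the last on-treatment day are both natural offsets if stop dates are included. On that reading nothing is lost.

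Much of this stands. A reader might infer from the table alone that AEs on the day of death, or on the day before first dose, do drop out of the AE tables. The document does not support that as the plan's settled result, because Section 7.8.1 gives both days a period. The day before first dose also has no bearing on the on-treatment tables, since such an event is pre-treatment under either rule. After the REP, events are for listings only, so no AE table loses them.

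The reply does not remove the contradiction. The heading says excluded, Section 6.1 uses the table to define the periods, and Section 7.8.1 defers to Section 6.1 for the details. Nothing in the SAP tells a programmer to prefer the text to the table.

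**Conclusion.** The point holds as a contradiction between Table 6.1: 1 and Section 7.8.1. The day of a death within the REP is the consequential case, and the day of last dose + 42 comes second. The remaining boundary days have minor effect.

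Loss of fatal AEs with same-day onset follows only if the table is programmed literally and periods are assigned by onset date. Its size cannot be stated from the document. The affected set is narrow: onset date equal to death date, with death inside the REP. A fatal AE that started on an earlier treatment day stays on-treatment under both rules.

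A reader might also infer that the errors always favour the drug. That fits the death-day gap, where fatal events can only be undercounted. It does not fit the first dosing day, where the table counts pre-infusion events as on-treatment.

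Severity is moderate. The AE analyses are descriptive, and both primary endpoints have their own windows in Section 5.1 (first cycle for dose limiting toxicities, a separate rule for objective response).

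**What to change.** - Relabel the stop column of Table 6.1: 1 as included. Screening then runs to first dose date − 1 day. On-treatment runs to the earliest of last dose + 42 days, death or DBL. Post-study runs from the next day to the earliest of last contact, death or DBL.
- Align the wording of Section 7.8.1 with the table, saying explicitly that the death day and the day of last dose + 42 are on-treatment.
- State one rule for events before the infusion on the first dosing day. The SAP does not say whether AE onset times are recorded, so the rule should also cover a missing time.

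The cost is a small edit to the SAP and to the period-derivation program, best made before database lock because it decides how fatal events are counted.
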